## 6.2 Conventions

Unless otherwise specified, in summary tables of continuous variables, the minimum and maximum values will be displayed to the same number of decimal places as the raw data, the mean and median will be presented to one extra decimal place compared to the raw data, and the standard deviation will be displayed to two extra decimal places compared to the raw data. Wherever possible data will be decimal aligned.

Unless otherwise specified frequency tabulations will be presented by number and percentage, where the percentage is presented in parenthesis to 1 decimal place.

P-values, if applicable, will be presented to 3 decimal places. If a p-value is less than 0.05 but is greater than or equal to 0.01, then an asterisk (\*) will be added next to this value. If a p-value is less than 0.01 but is greater than or equal to 0.001, then two asterisks (\*\*) will be added next to this value. Finally, if the p-value is less than 0.001 then three asterisks (\*\*\*) will be added next to this value and it will be presented as <0.001. If the rounded result is a value of 1.000, it will be displayed as >0.999. Any date information in the listing will use the *date9.* format, for example, 07MAY2002. In the listing, a unit associated with a variable will be presented only once within parentheses either below or next to that variable in the heading portion. If a parameter has multiple units, each unit will be displayed only once, as applicable.

All tables will have their source listing referenced in a footnote. Listings should be sorted by dose level or treatment group, subject and visit and have the source data received by data

management referenced in a footnote. All tables and listings will be converted into Microsoft Word documents and collated into two complete documents.

## 6.3 Tables

### 6.3.1 Section 14.1: Demographic and baseline

Table 14.1.1.1	Subject Disposition – Part A (Enrolled Population)
Table 14.1.1.2	Subject Disposition – Part B (Enrolled Population)
Table 14.1.1.3	Important Protocol Violations – Part A (Enrolled Population)
Table 14.1.1.4	Important Protocol Violations – Part B (Enrolled Population)
Table 14.1.2.1	Demographics – Part A (Safety Population)
Table 14.1.2.2	Demographics – Part B (Safety Population)
Table 14.1.3.1	Medical History – Part A (Safety Population)
Table 14.1.3.2	Medical History – Part B (Safety Population)
Table 14.1.4.1	Cancer History – Part A (Safety Population)
Table 14.1.4.2	Cancer History – Part B (Safety Population)
Table 14.1.5.1	Prior Cancer Therapies – Part A (Safety Population)
Table 14.1.5.2	Prior Cancer Therapies – Part B (Safety Population)
Table 14.1.6.1	Concomitant Medications – Part A (Safety Population)
Table 14.1.6.2	Concomitant Medications – Part B (Safety Population)
Table 14.1.7.1	Other Anti-Cancer Medications – Part A (Safety Population)
Table 14.1.7.2	Other Anti-Cancer Medications – Part B (Safety Population)
Table 14.1.8.1.1	Summary of Exposure to BGB324 – Part A (Safety Population)
Table 14.1.8.1.2	Summary of Exposure to BGB324 – Part B (Safety Population)
Table 14.1.8.2	Summary of Exposure to Cytarabine – Part B (Safety Population)
Table 14.1.8.3	Summary of Exposure to Decitabine – Part B (Safety Population)
Table 14.1.9.1.1	Compliance – Part A (Safety Population)
Table 14.1.9.1.2	Compliance – Part B (Safety Population)
Table 14.1.9.2.1	Summary of BGB324 dose reduction and dose interruption – Part A (Safety Population)
Table 14.1.9.2.2	Summary of BGB324 dose reduction and dose interruption – Part B (Safety Population)
Table 14.1.10.1.1	Summary of BGB324 Dose Modification during the Study – Part A (Safety Population)
Table 14.1.10.1.2	Summary of BGB324 Dose Modification during the Study – Part B (Safety Population)

### 6.3.2 Section 14.2: Efficacy Analysis

Table 14.2.1.1	Objective Response Rate – Part A (Efficacy Population)
Table 14.2.1.2	Objective Response Rate – Part B (Efficacy Population)
Table 14.2.2.1	Relapse Free Survival – Summary – Part B (Efficacy Population)
Table 14.2.3.1	Event Free Survival – Summary – Part B (Efficacy Population)
Table 14.2.4.1	Overall Survival – Kaplan Meier Analysis – Part B (Efficacy Population)

Table 14.2.5.1.1	Objective Response Rate by Age Group – Part A (Efficacy Population)
Table 14.2.5.1.2	Objective Response Rate by Age Group – Part B (Efficacy Population)
Table 14.2.5.1.3	Objective Response Rate by AML Disease Cytogenetic profile – Part A (Efficacy Population)
Table 14.2.5.1.4	Objective Response Rate by AML Disease Cytogenetic profile – Part B (Efficacy Population)

### 6.3.3 Section 14.3: Safety Analysis

#### 6.3.3.1 Adverse events

Table 14.3.1.1.1	Summary of Adverse Events – Part A (Safety Population)
Table 14.3.1.1.2	Summary of Adverse Events – Part B (Safety Population)
Table 14.3.1.2.1.1	Adverse Events by System Organ Class and Preferred Term – Part A (Safety Population)
Table 14.3.1.2.1.2	Adverse Events by System Organ Class and Preferred Term – Part B (Safety Population)
Table 14.3.1.2.2.1	Adverse Events by System Organ Class, Preferred Term, and CTCAE Grade – Part A (Safety Population)
Table 14.3.1.2.2.2	Adverse Events by System Organ Class, Preferred Term, and CTCAE Grade – Part B (Safety Population)
Table 14.3.1.2.3.1	Adverse Events Related to BGB324 by System Organ Class and Preferred Term – Part A (Safety Population)
Table 14.3.1.2.3.2	Adverse Events Related to BGB324 by System Organ Class and Preferred Term – Part B (Safety Population)
Table 14.3.1.2.4	Adverse Events Related to Cytarabine by System Organ Class and Preferred Term (Safety Population)
Table 14.3.1.2.5	Adverse Events Related to Decitabine by System Organ Class and Preferred Term (Safety Population)
Table 14.3.1.2.6.1	Adverse Events Related to Other Anti-Cancer Medications by System Organ Class and Preferred Term – Part A (Safety Population)
Table 14.3.1.2.6.2	Adverse Events Related to Other Anti-Cancer Medications by System Organ Class and Preferred Term – Part B (Safety Population)
Table 14.3.1.2.7.1	Adverse Events by System Organ Class, Preferred Term and Frequency CTCAE Grade – Part A (Safety Population)
Table 14.3.1.2.7.2	Adverse Events by System Organ Class, Preferred Term and Frequency CTCAE Grade – Part B (Safety Population)
Table 14.3.1.3.1.1	Serious Adverse Events by System Organ Class and Preferred Term – Part A (Safety Population)
Table 14.3.1.3.1.2	Serious Adverse Events by System Organ Class and Preferred Term – Part B (Safety Population)
Table 14.3.1.3.2.1	Serious Adverse Events by System Organ Class, Preferred Term, and CTCAE Grade – Part A (Safety Population)
Table 14.3.1.3.2.2	Serious Adverse Events by System Organ Class, Preferred Term, and CTCAE Grade – Part B (Safety Population)
Table 14.3.1.3.3.1	Serious Adverse Events Related to BGB324 by System Organ Class and Preferred Term – Part A (Safety Population)

Table 14.3.1.3.3.2	Serious Adverse Events Related to BGB324 by System Organ Class and Preferred Term – Part B (Safety Population)
Table 14.3.1.3.4	Serious Adverse Events Related to Cytarabine by System Organ Class and Preferred Term (Safety Population)
Table 14.3.1.3.5	Serious Adverse Events Related to Decitabine by System Organ Class and Preferred Term (Safety Population)
Table 14.3.1.3.6.1	Serious Adverse Events Related to Other Anti-Cancer Medications by System Organ Class and Preferred Term – Part A (Safety Population)
Table 14.3.1.3.6.2	Serious Adverse Events Related to Other Anti-Cancer Medications by System Organ Class and Preferred Term – Part B (Safety Population)
Table 14.3.1.4.1.1	Adverse Events Leading to Discontinuation by System Organ Class and Preferred Term – Part A (Safety Population)
Table 14.3.1.4.1.2	Adverse Events Leading to Discontinuation by System Organ Class and Preferred Term – Part B (Safety Population)
Table 14.3.1.5.1.1	Adverse Events >= Grade 3 by System Organ Class and Preferred Term – Part A (Safety Population)
Table 14.3.1.5.1.2	Adverse Events >= Grade 3 by System Organ Class and Preferred Term – Part B (Safety Population)
Table 14.3.1.5.2.1	Adverse Events >= Grade 3 Related to BGB324 by System Organ Class and Preferred Term – Part A (Safety Population)
Table 14.3.1.5.2.2	Adverse Events >= Grade 3 Related to BGB324 by System Organ Class and Preferred Term – Part B (Safety Population)
Table 14.3.1.5.3	Adverse Events >= Grade 3 Related to Cytarabine by System Organ Class and Preferred Term (Safety Population)
Table 14.3.1.5.4	Adverse Events >= Grade 3 Related to Decitabine by System Organ Class and Preferred Term (Safety Population)
Table 14.3.1.6.1	Adverse Events Occurring >= 10% by Preferred Term – Part A (Safety Population)
Table 14.3.1.6.2	Adverse Events Occurring >= 10% by Preferred Term – Part B (Safety Population)
Table 14.3.1.7.1	Non-Serious Adverse Events by System Organ Class and Preferred Term – Part A (Safety Population)
Table 14.3.1.7.2	Non-Serious Adverse Events by System Organ Class and Preferred Term – Part B (Safety Population)
Table 14.3.1.8.1	Adverse Events leading to death by System Organ Class and Preferred Term – Part A (Safety Population)
Table 14.3.1.8.2	Adverse Events leading to death by System Organ Class and Preferred Term – Part B (Safety Population)
Table 14.3.1.9.1	Summary of DLTs occurring during the study – Part A (Safety Population)
Table 14.3.1.10.1	Adverse Events beyond disease progression by System Organ Class and Preferred Term – Part B (Safety Population)
Table 14.3.1.10.2	Serious Adverse Events beyond disease progression by System Organ Class and Preferred Term – Part B (Safety Population)

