9.2.1.1. Dose Escalation Scheme

Initially three patients will be recruited into Cohort 1 and will complete 1 cycle of treatment before a dose-escalation evaluation is made. A patient must receive all loading doses and miss no more than 3 maintenance doses in Cycle 1 in order to be considered as informative to support dose escalation, unless the missed doses are due to bemcentinib toxicity (see Section 9.2.1.2. Dose Limiting Toxicity).

The decision to dose-escalate (or not) will be made by the SMC comprising a representative from each actively recruiting investigational site and a representative of the BerGenBio ASA study team. Minutes of the SMC meeting will be recorded and circulated for final approval before being placed in the Trial Master File (TMF). The decision to dose escalate will be based upon the tolerability of bemcentinib.

Where dose escalation occurs, 3 patients will be recruited to the next cohort (dose level) and will complete 1 cycle of treatment before a dose-escalation evaluation is made, as outlined above.

If one patient in a cohort experiences a DLT during Cycle 1, the cohort will be expanded to 6 patients. If 2 of 3 or 2 of 6 patients in a cohort experience DLT no further dose-escalation will take place and the dose below will be nominated as the MTD. If the starting dose exceeds the MTD, a lower dose may be explored if recommended by the SMC. Provided treatment with the starting dose is considered safe by the SMC according to DLT evaluation, dose escalation may proceed.

Possible dosing levels are illustrated in Table 3. Dosing with Formulation 2 will consist of a loading dose of 200 mg administered on Days 1, 2 and 3 followed by a daily maintenance dose of 100 mg. This dose may be escalated as agreed by the SMC to a maximum daily loading dose of 400 mg on Days 1, 2 and 3 followed by a maximum daily maintenance dose of 200 mg. The maximum daily dose that may be explored in this study will be 400 mg.

Table 3: Possible Bemcentinib Dosing Levels Involving A Loading Dose and Daily Dose for Part A

[figure not shown]
Total Loading Dose over 3 days (mg)	Days 1, 2 and 3 Loading Dose (mg)	Daily maintenance dose (mg)
600	200*	100*
1200	400	200

*starting dose

If a patient withdraws or is withdrawn for reasons other than DLT prior to completing Cycle 1, the patient will be replaced for the purposes of toxicity evaluation.

Please refer to Figure 6 for the operating characteristics of the Dose Escalation process.

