## Dose Escalation Scheme

Initially three patients will be recruited into Cohort 1 and will complete 1 cycle of treatment before a dose-escalation evaluation is made. A patient must receive all loading doses and miss no more than 3 standard doses in Cycle 1 in order to be considered as informative to support dose escalation, unless the missed doses are due to bemcentinib toxicity.

The decision to dose-escalate (or not) will be made by the SMC comprising a representative from each actively recruiting investigational site and a representative of the BerGenBio AS study team. Minutes of the SMC meeting will be recorded and circulated for final approval before being placed in the Trial Master File (TMF). The decision to dose escalate will be based upon the tolerability of bemcentinib observed at the previous dose level. Dose escalation will range between 25% and 50% of the previous dose according to the nature and severity of the toxicity observed.

Where dose escalation occurs, three patients will be recruited to the next Cohort (dose level) and will complete 1 cycle of treatment before a dose-escalation evaluation is made, as outlined above.

If one patient in a cohort experiences a DLT during Cycle 1, the cohort will be expanded to six patients. If two of three or two of six patients in a cohort experience DLT no further dose-escalation will take place and the dose below will be nominated as the MTD. If the starting dose exceeds the MTD, a lower dose may be explored if recommended by the SMC. Provided treatment with the starting dose is considered safe by the SMC according to DLT evaluation, dose escalation may proceed.

The maximum daily dose that may be explored in this study will be 400 mg.

If a patient withdraws or is withdrawn for reasons other than DLT prior to completing Cycle 1, the patient will be replaced for the purposes of toxicity evaluation.

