### 4.5.2 Safety Analysis Population

The Safety analysis population will be defined as all enrolled patients who receive at least one dose of bemcentinib. The Safety analysis population will be analysed by dose group or combination in Part B.

Patients enrolled to Part A who meet the eligibility criteria for Part B1 and who receive the MTD and/or RP2D, may contribute to the Part B1 analysis.

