## 4.6 Withdrawn Subjects

Patients may withdraw informed consent and discontinue from the study at any time, or for any reason, without prejudice to their future treatment. In addition, a patient must be discontinued from the study if any of the following criteria are met:

- Patient non-compliance with the protocol, as agreed by the investigator and the sponsor
- Patient lost to follow-up
- Termination of the study by the sponsor
- Patient experiences an unacceptable toxicity that precludes them from continuing in the study e.g. patient experiences a ventricular arrhythmia (see study protocol Section 12.2), as agreed by the investigator and the sponsor

- Lack of adequate recovery from a DLT, see Section 9.2.1.2 in study protocol
- Failure of toxicity to adequately resolve, as outlined in Section 12.2 in study protocol
- Female patient becomes pregnant
- Patient experiences clinical disease progression
- Patient and/or investigator decision

AEs resulting in discontinuation will be followed as outlined in study protocol Section 9.3.4.

Patients who discontinue during the DLT assessment period (Part A), for any reason other than a DLT, will be replaced. All other patients who discontinue study treatment will not be replaced.

If a patient discontinues treatment prior to study completion, and for reasons other than progression or non-tolerability, every effort should be made to conduct the Final Study Visit assessments as outlined in Section 11.5 of the protocol. The reason for the patient's withdrawal from the study must be recorded in the eCRF.

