## 5 Statistical Methodology

### 5.1 Planned Analyses

Disposition analyses will be carried out using the Enrolled Population. Demographic and baseline characteristics analyses will be carried out using the Safety Analysis Set. Safety analyses will be carried out using the Safety Analysis Set. Efficacy analyses will be carried out using the Efficacy Analysis Population.

Summary statistics will be presented for continuous variables, by way of n, mean, standard deviation (SD), median, minimum (Min) and maximum (Max) and by way of group frequencies and percentages for categories of categorical variables. No statistical comparison of dose levels or treatment groups will be performed. Percentages will be calculated using the total patients per dose cohort in the given population unless otherwise noted.

All data from this study will be presented in data listings. All listings will be sorted by dose level or treatment group and patient.

Baseline will be defined as the last assessment prior to study drug administration. Typically this will be Cycle 1 Day 1. Where calculated, absolute change from baseline will be presented using the following formula for each parameter: Value at the visit/timepoint – value at baseline.

Data will be presented by dose/cohort and overall in Part A and by treatment group (AML (B1: BGB324 400/200 mg Single agent; B2: BGB324 400/200 mg + Cytarabine; B3: BGB324 400/200 mg + Decitabine; B5: BGB324 400/200 mg + Cytarabine) and MDS (B4: BGB324 400/200 mg) ) and overall in Part B.

Where appropriate, the data for patients who received the MTD during Part A will be combined with that for patients who received the MTD in Part B for the purpose of data summarisation. A clear distinction will be made in the relevant Tables to differentiate between the cohort who received the MTD during the dose escalation phase of Part A, the MTD cohort from the cohort expansion phase in Part A, and the combined MTD cohort.

Any patient treated with bemcentinib beyond disease progression will be followed for the same safety and efficacy assessments as for all other patients enrolled into the study. The data for patients treated beyond progression will be presented in both a combined output (with all patients) and a separate output (reflecting a new period of analysis with the data collected in this period). All data collected will be included in the study CSR and may be presented at congress/symposia.

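### The only planned DLT table counts all dosed patients, so a Part A cohort with a DLT and a dosed but non-informative patient will show a rate below the fraction behind the 3+3 decision

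*SAP*

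**What the plan says.** **Who counts for escalation.** SAP 4.1 (Dose Escalation Scheme) sets the rule: "A patient must receive all loading doses and miss no more than 3 standard doses in Cycle 1 in order to be considered as informative". Protocol 9.2.1.1 has the same rule for maintenance doses: "miss no more than 3 maintenance doses in Cycle 1 in order to be considered as informative to support dose escalation". Both exempt doses missed because of bemcentinib toxicity.

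**Who is replaced.** Protocol 9.2.1.1 says of a patient who withdraws before completing Cycle 1 for a reason other than DLT that "the patient will be replaced for the purposes of toxicity evaluation". SAP 4.6 agrees: "Patients who discontinue during the DLT assessment period (Part A), for any reason other than a DLT, will be replaced".

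**What is tabulated.** SAP 6.3.3.1 lists one DLT table, 14.3.1.9.1, titled "Summary of DLTs occurring during the study – Part A (Safety Population". SAP 4.5.2 defines that set: "The Safety analysis population will be defined as all enrolled patients who receive at least one dose of bemcentinib". A closing line in SAP 6.3.3.5 puts every safety table on it. SAP 5.1 gives the denominator: "Percentages will be calculated using the total patients per dose cohort in the given population unless otherwise noted". SAP 6.2 makes number and percentage the default display.

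**What is absent.** SAP 4.5 defines Enrolled, Safety and Efficacy populations and drops the per-protocol set. It has no DLT-evaluable set. The DLT listing, 16.2.7.8, is also on the Safety Population.

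**The concern.** Finding the MTD is the Part A primary objective, and the DLT profile is its first secondary objective. Under the 3+3 rule, both are read from DLT counts among informative patients. Following the defaults, the CSR table counts a dosed patient who was replaced, or who was otherwise non-informative, as a treated patient without a DLT. The escalation rule treats that patient as carrying no information. The tabulated percentage can then only equal or fall below the fraction on which the SMC acted. A reader of the CSR could not recover that fraction from the table.

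**Working it through.** **1. Reproduce the plan's own figures.** SAP 4.9 (Table 1) and protocol 16.9 (Table 16) give escalation probabilities for a rule that escalates on 0/3 or 1/6. With true DLT rate p:

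P(escalate) = (1−p)³ + 3p(1−p)² × (1−p)³

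| p | Terms | Result | Plan |
|---|---|---|---|
| 0.20 | 0.5120 + 0.1966 | 0.709 | 71% |
| 0.30 | 0.3430 + 0.1513 | 0.494 | 49% |
| 0.40 | 0.2160 + 0.0933 | 0.309 | 31% |
| 0.50 | 0.1250 + 0.0469 | 0.172 | 17% |
| 0.60 | 0.0640 + 0.0184 | 0.082 | 8% |

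Every row matches. The formula treats all 3 or 6 patients as evaluable for DLT, so the stated properties belong to the informative set and not to all dosed patients.

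**2. Compare the two denominators.** Let d be the patients with a DLT, n the informative patients in the cohort, and k the dosed patients without a DLT who are replaced or non-informative.

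- Fraction behind the decision: d/n.
- Table rate under the SAP defaults: d/(n+k), which equals (d/n) × n/(n+k).

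These k patients add nothing to the numerator. The table rate therefore equals d/n when k = 0 or d = 0, and is lower otherwise.

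**3. Put in numbers.** The documents do not give k. I assume 0 to 3.

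| Cohort result | k = 0 | k = 1 | k = 2 | k = 3 |
|---|---|---|---|---|
| 1/6 (escalate) | 16.7% | 1/7 = 14.3% | 1/8 = 12.5% | 1/9 = 11.1% |
| 2/6 (stop) | 33.3% | 2/7 = 28.6% | 2/8 = 25.0% | 2/9 = 22.2% |
| 2/3 (stop) | 66.7% | 2/4 = 50.0% | 2/5 = 40.0% | 2/6 = 33.3% |

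**4. Check who makes up k.** Protocol 9.2.1.1 and SAP 4.1 replace patients who withdraw. They do not say that a patient who stays in Cycle 1 but misses too many doses is replaced. Both kinds of patient enter the Safety Population denominator, so k includes both.

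**5. Check the time window.** The table title refers to the whole study. Protocol 9.2.1.2 and SAP 4.1 (Dose Limiting Toxicity) assess DLTs over the first 3 weeks (Cycle 1), yet one listed criterion concerns blood counts after Day 42. Those two statements do not fit together. Limiting the table to Cycle 1 would drop that criterion and could lower the numerator.

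**The case against.** Several points on the other side have force.

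- **The dilution is conditional.** The documents do not say that any dosed Part A patient was replaced or non-informative. This stands: the size is an assumption, and the effect may be zero.
- **The table itself is not shown.** Its layout is in a separate shells file named in SAP 6.5, and the denominator rule in SAP 5.1 allows exceptions. This leaves some room. However, the table title and the closing line of SAP 6.3.3.5 both name the Safety Population, and the SAP notes no exception.
- **The MTD does not come from this table.** Under protocol 9.2.1.1 and 16.8, the SMC decides from Cycle 1 data per cohort. Protocol 16.8 also records Part A as fully completed in its status as of 17 March 2020, and the shells are dated 6 September 2022. A reader might infer that the MTD or an escalation step is biased. The documents do not support that.
- **The protocol promises only a DLT listing** (16.4.2), and DLTs among all treated patients is a legitimate description. This is true, but it is a different quantity from the one the 3+3 rule uses, and no table gives the latter.
- **The fraction can be pieced together** from cohort assignment, disposition, dosing and DLT listings (SAP 6.4). This holds in part, but the reader would have to apply the informative rule patient by patient.
- **An evaluable set need not return x/3 or x/6**, because 6 to 10 patients are to be treated at the MTD or RP2D. This is true at that level. SAP 5.1 already requires the escalation and expansion MTD cohorts of Part A to be told apart in the relevant tables.

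**Conclusion.** The point holds as a reporting defect. On the SAP's stated defaults, Table 14.3.1.9.1 uses a denominator that differs from the one behind the 3+3 decisions. The tabulated DLT rate is lower whenever a cohort has both a DLT and a dosed patient who is non-informative or replaced. With 1 to 3 such patients assumed, a 2/6 cohort loses 4.7 to 11.1 percentage points (33.3% to between 28.6% and 22.2%). A 1/6 cohort loses 2.4 to 5.6 points (16.7% to between 14.3% and 11.1%). With no such patient, or no DLT, the two rates agree.

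Two stronger readings should be resisted. The documents do not show that the reported rate will in fact be too low, since the number of affected patients is unknown and the shells were not available. Nor do they show any effect on the SMC's decisions. The change is worth making because it is cheap and concerns the main Part A result, but nothing in the conduct of the trial depends on it.

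**What to change.** 1. Add a DLT-evaluable population to SAP 4.5: Part A patients who are informative under protocol 9.2.1.1, plus any patient with a DLT.
2. Base Table 14.3.1.9.1 on that population, by dose level.
3. List the dosed patients left out with reasons, separating those replaced from those who were non-informative but stayed on study.
4. Keep the other Part A safety tables and DLT listing 16.2.7.8 on the Safety Population.
5. Do not restrict the table to Cycle 1. Tie its window to the protocol's DLT definition, and reconcile the 3-week (Cycle 1) assessment period with the criterion assessed after Day 42, which appears in both protocol 9.2.1.2 and SAP 4.1.

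The cost is SAP wording and one flag variable. No new data should be needed, since the SMC already had to apply the informative rule. Reported DLT percentages may look slightly less favourable.

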9.3.2.1 Dosing patients beyond progression

An important clinical observation in the last decade is that immune activation does not necessarily result in complete cancer regression for all patients, but nonetheless, clinical improvements are observed. In this context and for elderly patients with R/R AML, unfit for intensive chemotherapy and with no alternative treatments available for their disease, achieving stable disease and/or becoming transfusion independent, together with performance status improvement, can be viewed as a positive signal. Thus, where in the investigator's opinion, the patient's disease is considered "clinically stable" with clear improvement in the patient's symptomatology and with no other treatment options available,

other than palliative care, it may be in the patient's best interests to remain on treatment with bemcentinib.

Therefore, patients experiencing disease progression are permitted to continue treatment with bemcentinib where the investigator believes patients may continue to derive clinical benefit from continued treatment.

Clinical benefit in this context is defined as meeting one or several of the following criteria: evidence of disease stabilization after documented initial progression (patient is stably worse), tolerance of drug(s), absence of rapid progression based on peripheral or bone marrow blasts and clinical hematology and clinical chemistry parameters, maintenance of good performance status (PS of 2 or less and not deteriorating], absence of worsening clinical symptoms (i.e., no symptomatic deterioration) and/or improvements in patient's quality of life).

Importantly, the decision to continue treatment must be discussed and agreed by the treating investigator, the patient and the Sponsor. All decisions will be documented in writing. Patients dosed beyond progression will continue to be evaluated for potential clinical benefit and safety. This will not affect the time point of disease progression from the perspective of trial analysis.

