For subjects in Part B a new period (treated beyond disease progression) will be created if the date of progression < date of any intake of the bemcentinib, to identify patient treated with bemcentinib beyond disease progression and also the visit cycle where the data are collected beyond the disease progression. The data collected during this period will be identified to be added in this analysis.

For Part B analysis, some outputs such as disposition, demographic and baseline characteristics, cancer history, ORR, AE and ECG(QtCF), the data for cohort B2 and B5 will be summarized together.

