### 6.3.3.5 ECOG Performance Status

Table 14.3.5.7.1.1	Eastern Cooperative Oncology Group (ECOG) Performance Status – Part A (Safety Population)
Table 14.3.5.7.1.2	Eastern Cooperative Oncology Group (ECOG) Performance Status – Part B (Safety Population)

All safety tables will be produced using the Safety Population.

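### The tables of AEs and SAEs beyond disease progression divide by every dosed Part B patient, so they understate incidence among those at risk by a factor (N/m) that the documents do not fix

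*SAP*

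**What the plan says.** Protocol 9.3.2.1 lets patients stay on bemcentinib after progression case by case: "the decision to continue treatment must be discussed and agreed by the treating investigator, the patient and the Sponsor". It says that these patients will go on being evaluated for benefit and safety. SAP 5.1 (as does Protocol 16.4.2) promises their data twice, once pooled with all patients and once as "a separate output (reflecting a new period of analysis with the data collected in this period").

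SAP 5.1 also says who is in that period. For Part B subjects, "a new period (treated beyond disease progression) will be created if the date of progression < date of any intake of the bemcentinib".

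SAP 6.3.3.1 lists two tables for the period. The one for all AEs is titled "Adverse Events beyond disease progression by System Organ Class and Preferred Term – Part B (Safety Population"); it is numbered 14.3.1.10.1. The one for SAEs, numbered 14.3.1.10.2, has a parallel title and is assigned to the same Part B population.

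Three further statements govern the denominator:
- SAP 4.5.2: "The Safety analysis population will be defined as all enrolled patients who receive at least one dose of bemcentinib".
- SAP 5.1: "Percentages will be calculated using the total patients per dose cohort in the given population unless otherwise noted".
- SAP 6.3.3.5: "All safety tables will be produced using the Safety Population".

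SAP 4.5 defines no set of patients who entered the period, and nothing in the SAP notes a different denominator for these two tables.

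**The concern.** A patient who never progressed, or who stopped bemcentinib at progression, has no time in the period and cannot have an event in it. Under the SAP's rules that patient still counts in the denominator and so has the same effect as a patient who was observed in the period and stayed event-free.

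Safety and tolerability is the primary objective of Part B (Protocol 8.1.1). These are the only two summary tables listed for the period; the only other dedicated output is Listing 16.2.7.10. A separate output is meant to describe what happened to patients who continued. A percentage of all dosed patients does not do that, and without m in the table a reader cannot convert it. In a cohort where nobody continued, the table would show 0% when nothing had been observed.

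**Working it through.** The documents state no rate, sample size or expected percentage for these tables, so there is no planned figure to reproduce. The check follows the denominator through the SAP's rules and then does the arithmetic.

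**Step 1. Which denominator the text gives.** The table titles and SAP 6.3.3.5 name the Safety Population. SAP 4.5.2 sets one condition for it, at least one dose, with nothing about progression or later dosing. SAP 5.1 then divides by the cohort total in that population. The denominator is N, all dosed patients in the cohort. SAP 4.5.2 also allows some Part A patients to contribute to the B1 analysis, which could enlarge N for B1.

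**Step 2. Who can be in the numerator.** Under the period rule in SAP 5.1, only Part B patients with a bemcentinib intake dated after progression. Call their number m, and let k of them have the event.

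**Step 3. Formulas.**
- Percentage as planned: k/N
- Incidence among those at risk: k/m
- Ratio of the second to the first: (k/m)/(k/N) = N/m = 1/f, where f = m/N

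The ratio does not depend on k. It equals 1 only if every dosed patient in the cohort entered the period, and exceeds 1 otherwise.

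**Step 4. Size.** The documents do not give f, so the values below are assumptions that span the range.

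| Share dosed beyond progression, f | Understatement, 1/f |
|---|---|
| 10% | 10-fold |
| 20% | 5-fold |
| 25% | 4-fold |
| 33% | 3-fold |
| 50% | 2-fold |
| 75% | 1.3-fold |
| 100% | none |

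**Step 5. Illustrations.** The N values are the planned caps on evaluable patients (SAP 4.9) and stand in for the Safety Population, which may differ. The values of m and k are hypothetical.
- All of Part B: N = 4 × 14 + 20 = 76. With m = 19 and k = 10, the table shows 10/76 = 13.2%; among those at risk it is 10/19 = 52.6%.
- Part B5: N = 20. With m = 10 and k = 5, 5/20 = 25% against 5/10 = 50%.
- A 14-patient cohort with m = 3 and k = 2: 2/14 = 14.3% against 2/3 = 66.7%.
- The same cohort with m = 10 and k = 5: 5/14 = 35.7% against 5/10 = 50%.

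**The case against.** **The population label may only name the parent set.** The cytarabine and decitabine tables are also labelled Safety Population, yet SAP 5.8.1.1 confines them to Part B2 and Part B3. That is so, but the restriction there is by cohort, and the per-cohort rule in SAP 5.1 already gives the right denominator. Patients beyond progression are a subset within each cohort, which that rule does not reach.

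**The table shells may show another N.** They are a separate file, named in SAP 6.5, which was not available here, so this cannot be checked. If they do, they depart from the SAP's own text, which would still need correcting.

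**The subset is already identified and the raw information is visible.** This stands in part. SAP 5.1 gives a workable flag, SAP 6.2 prints counts beside percentages, and Listing 16.2.7.10 lists the events. None of these depends on the denominator, but none corrects the percentages either.

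**Two stronger readings are tempting, and the documents support neither.**
- A reader might infer that the understatement must be several-fold. That depends on f, and the text points both ways. Continuation needs three-party agreement, and SAP 4.6 lists clinical progression as a reason to discontinue, which suggests a small share. But the criteria for continuing in Protocol 9.3.2.1 are broad, and with daily dosing a single intake after the progression date is enough to enter the period, which suggests a larger one.
- A reader might infer that continued dosing will look far safer than dosing before progression. The SAP plans no such comparison; the safety analysis is descriptive. Correcting the denominator would not make that comparison valid either, because exposure times differ, the continuing patients are selected, and the combined output contains the same post-progression events.

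**Conclusion.** The point holds as a denominator error in the SAP text. As written, Tables 14.3.1.10.1 and 14.3.1.10.2 report k/N where the incidence among patients who could have the event is k/m. The direction is certain whenever any dosed patient in the cohort did not enter the period. The size is N/m and cannot be stated from the documents; over the shares considered it runs from 10-fold at 10% to none at 100%, and reaches 3-fold only if about a third or fewer of the cohort continued.

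This rests on reading the default rule in SAP 5.1 as applying to these tables, since no exception is noted, and on the unseen shells not setting a different N. Counts, the listing and the main AE tables are not affected, and no hypothesis test depends on it. It should still be corrected, because these two tables are the only planned summaries of adverse events in the period.

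**What to change.** 1. In SAP 4.5, define a treated-beyond-progression subset of the Part B Safety Population, using the flag already described in SAP 5.1.
2. Make its size per cohort, and overall, the denominator of Tables 14.3.1.10.1 and 14.3.1.10.2, and change their titles to match.
3. Exempt these two tables from the statement in SAP 6.3.3.5 that all safety tables use the Safety Population.
4. Show the period N and the days of exposure in the period in the column header or a footnote. Exposure matters because one dose after the progression date is enough to enter the period. Where the period N is zero, show the percentage as not applicable.

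The cost is one definition, one exempting sentence and two table headers, with the shells aligned to them. The flag is already to be derived, so no new data are needed.
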